9.8.4 Posture and Physical Activity

Subjects will be allowed to engage in normal activity.

9.9 Sample Collection and Processing

Over the course of the study, a blood sample will be collected at each visit (total of no more than 36 blood samples from each subject) for screening, safety laboratory and immunological assessments. Sample volume collected will vary between 15 mL and a maximum of 73 mL with individual samples collected into multiple tubes to facilitate disparate immunological tests (see table below for details).

A total of 8 blood samples will be collected for safety laboratory assessments from each subject, one sample at screening, pre-dose (within 60 minutes pre-dose), and 1, 7, and 14 days post dose for each dose (Days 1, 2, 8, 29, 30, 36). Each sample will consist of 15 mL of whole blood.

PD samples collected for immunogenicity assessment will 4 mL for T-cell analysis, 10 mL for ELISA, Luminex assay, virus neutralisation assay, and ADCC analysis, and 20 mL for isolation and cryopreservation of PBMCs. Pre-dose samples should be taken within 60 minutes of dosing, but all other samples may be taken within the visit window specified in Section 9.2.

Sample collections performed outside the pre-defined time windows are protocol deviations, however will be used for immunological, safety and statistical analyses. Unless otherwise specified, or for subject safety, when blood draws and other procedures coincide, blood draws will have precedence. Blood samples will be collected by direct venipuncture.

The total volume of blood including that collected for eligibility screening and safety purposes should not exceed 500 mL for the whole study, with up to 400 mL collected at visits between Day 1 and Day 57±2, and up to 100 mL collected at the Day 209±5 and 394±5 visits. All blood samples will be collected and processed as per the supplementary study specific laboratory manuals.

Table 1: Summary of all blood samples collected over the study Part 1 (Cohorts 1-3)

Visit	Total Collection Volume (mL)	Number of Samples Collected and Purpose of Sample			
		Safety Lab (15 mL)	PD (3-4 ml Whole blood)	PD (8-10 mL Serum)	PD 10-20 mL PBMCs)
Screening	29	1	1	1	0
Day 1 (first dose)	63	1	2	2	1
Day 2	15	1	0	0	0
Day 8	39	1	1	0	1
Day 15	34	0	1	1	1
Day 29 (second dose)	49	1	1	1	1
Day 30	15	1	0	0	0
Day 36	43	1	2	0	1
Day 43	34	0	1	1	1
Day 57	59	1	1	2	1
Day 120	10	0	0	1	0
Day 209	40	0	0	2	1
Day 394	20	0	0	2	0
Total volume	450				

Table 2: Summary of all blood samples collected over the study Part 2 (Cohorts 4-6)

Visit	Total Collection Volume (mL)	Number of Samples Collected and Purpose of Sample			
		Safety Lab (15 mL)	PD (3-4 ml Whole blood)	PD (8-10 mL Serum)	PD 10-20 mL PBMCs)
Screening	25	1	0	1	0
Day 1 (first dose)	63	1	2	2	1
Day 2	15	1	0	0	0
Day 8	39	1	1	0	1
Day 15	34	0	1	1	1
Day 29 (second dose)	45	1	0	1	1
Day 30	15	1	0	0	0
Day 36	39	1	1	0	1
Day 43	34	0	1	1	1
Day 57	55	1	0	2	1
Day 209	30	0	0	1	1
Day 394	10	0	0	1	0
Total volume	404				

9.9.1 Samples Storage

Samples collected for safety assessments will be retained by the central laboratory for 60 days after which they will be destroyed.

Samples collected for immunogenicity analysis will be retained by the bioanalytical labs for a maximum of 15 years after the study completion date.

9.10 Subject Monitoring

Subjects will be monitored throughout the study by the clinical staff for adverse events. A physician will be on site for treatment administration and until at least 2 hours post-dose, and available on call for the remainder of the study. If necessary, a physician, either at the clinical site or in a nearby hospital will administer treatment for any adverse event(s). A crash cart or emergency bag containing the necessary rescue material and appropriate medications will be available in the clinic to allow rapid intervention in case of emergency.

Subjects will be closely monitored by a medical team in the hours following dosing for the presence of symptoms of allergic or hypersensitivity reactions. Subjects will be also encouraged to quickly report any symptoms at any time they occur during the study period. The necessary rescue material, equipment, and appropriate medications will be available in the in the clinic to allow rapid intervention in case of emergency including, but not limited to:

- Oxygen;
- Adrenaline 1:1000 solution for IV or endotracheal injection;
- Antihistamines;
- Corticosteroids; and
- IV infusion solutions, tubing, catheters, and tape.

The following procedures will be followed in the event of a suspected anaphylactic reaction after dosing:

- Maintain an adequate airway.
- Administer antihistamines, adrenaline (epinephrine), or other medications as required by patient status and directed by the PI or a Medical Sub-Investigator.
- Continue to observe the patient and document observations.
- Emergency medical services may be called as needed.

Safety parameters, including laboratory results and ECG, will be assessed by a physician, using the clinical site's criteria for biomedical laboratory and ECG acceptance ranges as suggested guidelines in making the medical assessment. Abnormal safety laboratory results will be graded as mild, moderate or severe.

Scheduled safety measurements will be repeated according to the clinical site SOPs or upon request from a physician. Any abnormal repeated measurement will be evaluated by a physician and repeated if judged necessary. Further action may be taken upon physician's request.

Subjects will be advised to notify their health care professional(s) (e.g., physician, dentist, and/or pharmacist) that they are participating in a clinical research study on a treatment called SARS-CoV-2 Sclamp Vaccine, which is being developed for potential clinical use in the prevention of COVID-19 before taking any medicines or undergoing any medical procedure.

9.10.1 Vital Signs

BP, HR, RR, TT, and SpO₂ will be measured in a sitting position (except for safety reasons), at screening, pre-dose (each dose, Days 1 and 29), 24 hours post-dose (each dose, Days 2 and 30). Vital signs measurements should be performed before the blood collection whenever possible. Subjects should be seated for at least 5 minutes prior to taking measurements to allow for acclimatisation.

9.10.2 ECG

ECG will be performed at screening, before dosing (each dose, Days 1 and 29), and approximately 24 hours post-dose (each dose, Days 2 and 30). Subjects should recline in supine position for at least 5 minutes prior to taking measurements to allow for acclimatisation.

9.10.3 Physical Examination

A complete physical examination will be performed at screening. A complete physical examination includes assessments of the following: head, eyes, ears, nose, throat (HEENT), neck, chest, lungs, abdomen, musculoskeletal, dermatological, cardiovascular/peripheral vascular, and general neurological examination.

A brief physical examination will be done at pre-dose (each dose, Days 1 and 29). A brief physical examination includes assessments of the following: HEENT, chest, lungs, abdomen, dermatological, cardiovascular/peripheral vascular, and areas of note elicited from the subject.

9.10.4 Drug and Alcohol Screen

A urine drug screen (amphetamine, methamphetamine, methadone, barbiturates, benzodiazepines, cocaine, opiates, MDMA, PCP, and THC) and an alcohol breath test will be performed at screening and prior to each dosing.

9.10.5 Pregnancy Test

Where applicable i.e. for WOCBP, a serum pregnancy test will be performed at screening, and a urine pregnancy test will be performed pre-dose (each dose, Days 1 and 29). Where a positive urine pregnancy test is returned on Days 1 or 29, a serum pregnancy test will be undertaken for confirmation.

9.10.6 Laboratory Assessments

9.10.6.1 Tolerable Windows

Assessment value ranges, including those pertaining to haematology, biochemistry, coagulation, serology, and urinalysis are defined in Section 9.15.2. Subjects with values outside of these tolerable ranges will be assessed on a case-by-case basis by the PI to determine if follow-up is required for safety reasons.

To accommodate the various assessments a time window of ± 1 hour and ± 30 minutes will be allowed for pre and post-dose assessments respectively. Where applicable, blood collections will be prioritised ahead of other assessments (with an exception for vital signs, described in Section 9.10.1).

9.10.6.2 Haematology

Haematology will be performed at screening, before dosing (each dose, Days 1 and 29 ± 2), approximately 24 hours after each dosing (Day 2, Day 30 ± 1), Day 8 ± 1 , Day 36 ± 2 , Day 57 ± 2 . The following will be assessed: haemoglobin, haematocrit, RBC count, WBC count, neutrophils, lymphocytes, monocytes, eosinophils, basophils, platelet count.

9.10.6.3 Biochemistry

Biochemistry will be performed at screening, before dosing (each dose, Days 1 and 29 ± 2), approximately 24 hours after each dosing (Day 2, Day 30 ± 1), Day 8 ± 1 , Day 36 ± 2 , Day 57 ± 2 . The following will be assessed: albumin, amylase, lipase, creatine kinase, cholesterol, alkaline phosphatase, AST, ALT, GGT, urea, calcium, glucose random, magnesium, phosphate, potassium, creatinine, sodium, total bilirubin, LD, total protein, serum pregnancy (at screening and confirmation if a positive urine pregnancy test is returned on Days 1 and 29 ± 2), urine pregnancy Days 1 and 29 ± 2 , and FSH (at screening only).

9.10.6.4 Coagulation

Coagulation tests will be performed at screening, before dosing (each dose, Days 1 and 29 ± 2), approximately 24 hours after dosing (Day 2, Day 30 ± 1), Days 8 ± 1 , 36 ± 2 , and 57 ± 2 . The following will be assessed: prothrombin time (PT), partial prothrombin time (APTT), and fibrinogen.

9.10.6.5 Serology

Serology will be performed at screening. The following will be assessed: HIV 1 /2 and P24 antigen and antibody, hepatitis B surface antigen (HBsAg), and hepatitis C virus (HCV) antibody.

9.10.6.6 Urinalysis

Urinalysis will be performed at screening, before dosing (each dose, Days 1 and 29 ± 2), approximately 24 hours after each dosing (Day 2, Day 30 ± 1), Day 8 ± 1 , Day 36 ± 2 , Day 57 ± 2 . The

following will be assessed: microscopic examination, pH, specific gravity, protein, glucose, ketones, bilirubin, occult blood, nitrite, urobilinogen, and leukocytes.

9.10.6.7 SARS –CoV-2 Test

A SARS-CoV-2 test (nasal/oropharyngeal swab and RT-PCR and serum antibodies by ELISA) will be performed at screening, and Days 1–29 (nasal/oropharyngeal swab and RT-PCR only) and may also be performed on an *ad hoc* basis for subjects displaying, or reporting, symptoms characteristic of COVID-19 i.e. fever, dry cough, shortness of breath etc. at any time up to day 394.

9.10.7 Subject Self-Reporting

Subject self-reporting will occur throughout the study and will involve subjects being provided with access to an electronic diary (eDiary), or paper diary card (Diary), an oral thermometer, and a transparent, circular measuring device to provide safety information during periods when the subject is not present at the clinical site.

The electronic diary will be used from the time of first dose (Day 1) to 28 days post-second dose (Day 57±2), but may also be used during the 12 month follow-up period (up to Day 394±5) on an *ad hoc* basis if safety events arise. Subjects are required to complete daily reporting of solicited adverse events from Day 1 to Day 8, and Day 29 to Day 36. Subjects will use the diary to report spontaneous adverse events, concomitant medication use, doctor visits, and the COVID-19 symptoms as these events arise during study participation.

The oral thermometer will be used to provide subjects oral temperature, and the transparent, circular measuring device will be used to measure any local reactogenicity events i.e. redness, swelling etc. arising around the injection site. Training for the use of the oral thermometer and measuring device, as well as the electronic diary, will be provided on Day 1 following dosing.

When measuring oral temperature, subjects will be required to abstain from eating or drinking hot or cold foods and drinks for 30 minutes prior to each reading.

Examples of information captured via self-reporting will include both local (pain, swelling, redness etc.) and systemic events (fever, nausea, diarrhoea, fatigue, headache, muscle aches), as well as a prompt for symptoms of COVID-19, or potential recent exposure to SARS-CoV-2, or acquaintances diagnosed with COVID-19.

9.10.8 Injection Site Examination

An injection site examination will be performed at screening, pre-dose (each dose, Days 1 and 29), 30 minutes, and 24 hours post-dose (each dose, Days 2 and 30) to document the appearance. Subjects will be provided instructions on how to self-assess at home daily (from Days 1–8 and 29–36). An injection site examination site at screening will consist of examining the injection site (deltoid area of the subjects non-dominant arm), and making note of any skin reactions, disturbances, tattoos (on the deltoid area of the arm), or discolourations, for subject eligibility purposes. An injection site examination pre-dose will consist of examining the injection site and making note of the presence of any skin reactions, disturbances, or discolourations to establish a

baseline for assessment. An injection site examination post-dose will consist of examining the injection site and making note of the presence of any skin reactions, disturbances, or discolourations, such that they may be compared to the pre-dose examination. For each dose at pre-dose, 30 minutes, 24 hours, and 7 days post-dose, a trained observer, whom is blinded to the randomization scheme, will check and, as appropriate, record any local dermal reactions at the application site of note and review the eDiary/Diary with the subject.. When possible, the same evaluator will follow the subject throughout the study. In the event that more than one evaluator is required to follow the subject throughout the study, then every precaution should be taken to limit the number of evaluators.

9.11 Study Exit Procedures

Blood draws for immunogenicity assessments, and AE monitoring will be performed on the last study day (Day 394±5). In the event of discontinuance of a study subject leading to withdrawal from the study, all efforts will be made to complete study exit procedures within 14 days after the last participation of the subject in the study.

9.12 Data Collection and Evaluation

The clinical study site will use a validated EDC system to enter subject data onto electronic case report forms (eCRFs). Data will be collected using the EDC system and entered into a quality controlled clinical database. Prior to the commencement of the study, items to be included in the clinical database will be determined, and suitable paper source documents will be created to ensure the appropriate collection of all required data.

Clinical staff conducting the study will enter the required data promptly, accurately, legibly, and indelibly onto source documents. All entries, corrections, and alterations will be made by the Investigator or other authorized study personnel, and all data entries will be verified for accuracy and correctness. The EDC system is optimized for manual keying and review (including review by independent monitors) and maintains a full audit trail. All source documents will be conserved in order to maintain data integrity.

Clinical laboratory, PD, safety, and/or immunogenicity data will be transmitted electronically from external vendors to Data Management and reconciled against the clinical database. Further details of data management processes will be detailed in the data management plan.

9.13 Subject Withdrawal and Replacement

Subjects will be advised that they are free to withdraw from the study at any time. Over the course of the study, the Sponsor and the Investigator or a delegate may withdraw any subject from the study for one of the reasons described below; subject withdrawal will be done in accordance with the clinical site's SOP:

- Safety reason;
- Non-compliance with protocol requirements;
- Significant protocol deviation; or

- Positive alcohol breath test, urine drug screen, or pregnancy test;

Haematology, coagulation, and biochemistry results will be reviewed by the Investigator prior to dosing; subjects will be withdrawn from the study if it is deemed that the subject's safety may be at risk on the basis of these test results.

Subjects who withdraw, or are withdrawn, from the study prior to dosing, but after randomization, may be replaced. Subjects who withdraw, or are withdrawn, from the study after dosing will not be replaced. However, in the event that individual subjects drop out early into the study or the number of drop-outs exceeds initial expectations, subjects who withdraw, or are withdrawn, may be replaced at the discretion of the Sponsor. Such replacement resulting in dosing more subjects than planned in this protocol would be documented in a protocol amendment.

Subjects who withdraw, or are withdrawn, will be asked to remain at the clinic until the Investigator or a delegate agrees that the subject is fine and can be discharged. As soon as subject withdrawal is confirmed, blood sampling will be stopped. A PD blood draw may be collected at the time of withdrawal if deemed required by the Investigator. Study exit procedures will be performed at the time of withdrawal from the study, or as soon as possible thereafter.

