9.3 Randomisation and Blinding

Subjects will be administered either a cohort specific SARS-CoV-2 Sclamp vaccine or placebo (Treatment A, B, C, or D, see Section 9.5), according to the randomisation scheme produced by Syneos Health. Eligible subjects will be allocated a randomisation number associated with a randomised treatment prior to dosing, as close to dosing as feasible (Day 1) in order to minimise the number of subject withdrawals in the period between randomisation allocation and dosing.

The subjects and the clinical personnel involved in the collection, monitoring, revision, or evaluation of AEs, or personnel who could have an impact on the outcome of the study will be blinded with respect to the subject's treatment assignment (SARS-CoV-2 Sclamp vaccine or placebo). Except for circumstances related to subject safety (see Section 7.1), blinding will be maintained at least until data collection of all subjects in each cohort up to Day 57 i.e., when reporting and evaluation of all AEs have been completed up to 28 days post-second dose.

After data is collected for all subjects up to Day 57 the collected data will be locked and the treatment assignment will be unblinded to all study team members for the purpose of data analysis and generation of the Clinical Study Report (CSR) Part 1 and Addendum to the CSR Part 2. Subjects will remain blinded for the remaining duration of the study, thus the study will adopt a single-blind design after Day 57.

Designated pharmacy personnel at the clinical site not directly involved with the clinical aspects of the trial will prepare and dispense the study medication and will be aware of the randomisation code and the treatment.

In the event of an emergency for an individual subject in which knowledge of the study treatment is critical to the subject's medical management, or for the decision of dose escalation, the Investigator, or another attending study physician, will break the blind for that subject. An envelope for each subject containing their treatment assignment will be available from the pharmacy personnel. The Investigator, or other attending study physician, will make every effort to contact the Sponsor prior to unblinding a subject's treatment assignment and will record the date and reason for unblinding in the study source documents. In the event the Sponsor cannot be contacted prior to unblinding, the Sponsor will be contacted at the earliest feasible time after the unblinding has occurred.

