9.4 Allocation of Subjects to Treatment

Subjects will be randomly assigned a 4-digit randomisation number beginning by "1", "2", "3", "4", "5" and "6" for Cohorts 1, 2, 3, 4, 5 and 6 respectively. Each subject number corresponds to a treatment assignment on the generated randomisation scheme.

For Part 1 (healthy adults), the two sentinel subjects of each cohort will have the first two subject numbers of their cohort e.g. 1001 and 1002 for Cohort 1, and 2001 and 2002 for Cohort 2 and 3001 and 3002 for Cohort 3. In the case where a subject is replaced (following specifications described in Section 9.13), the replacement volunteer will take the same treatment and the same subject number added with 100. For example, if the subject number 1001 withdrew, the replacement subject will have the subject number 1101, with the treatment planned for the randomization number 1001.

For Part 2 (healthy older adults), subjects will be randomly assigned to treatment groups in a 3:1 ratio of Active to Placebo. The randomisation will be stratified by age (≥ 56 to ≤ 65 years, and ≥ 66 years respectively).

For subjects who are replaced, the replacements should take the same treatment assignment as the original subject to ensure that the planned treatment allocation ratio is retained.

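### If a dosed subject's code is broken and that subject is then replaced, the replacement's treatment is known before enrolment to whoever learned the code

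*Protocol*

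**What the plan says.** **Replacement (protocol Section 9.13).** The default for people who leave after dosing is firm: "Subjects who withdraw, or are withdrawn, from the study after dosing will not be replaced". An exception follows for early drop-out, or for more drop-out than expected: "subjects who withdraw, or are withdrawn, may be replaced at the discretion of the Sponsor". The section then adds: "Such replacement resulting in dosing more subjects than planned in this protocol would be documented in a protocol amendment". Since it foresees extra dosing, the exception must reach subjects who have already been dosed.

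**Allocation of the replacement (Section 9.4).** In the Part 1 paragraph, "the replacement volunteer will take the same treatment and the same subject number added with 100"; the worked example turns 1001 into 1101. A closing sentence, not limited to Part 1, says "the replacements should take the same treatment assignment as the original subject to ensure that the planned treatment allocation ratio is retained".

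**Breaking the blind (Sections 9.3 and 7.1).** Section 9.3 covers an emergency in which the treatment must be known, and continues: "or for the decision of dose escalation, the Investigator, or another attending study physician, will break the blind for that subject". The physician tries to reach the Sponsor beforehand, or informs it as soon as feasible afterwards. Section 7.1 describes a blinded SRC review in which individual codes may be opened before an escalation decision. The SRC has at least the Principal Investigator, one Sponsor representative and a medical monitor.

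**Who must stay blinded (Section 9.3).** Clinical staff who collect or evaluate adverse events, and anyone able to influence the outcome, are to be blind to treatment, with an exception for subject safety.

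**The concern.** Each rule is ordinary by itself. Together they let a code opened for one person disclose the treatment of another. The second person is a new volunteer with no safety event of their own, so the reason that justified opening the code does not apply to them.

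Two things are at stake. The first is concealment: several eligibility criteria in Section 8.4 rest on the Investigator's opinion, and the Sponsor decides whether to replace at all. Either could be acting with the arm known. The second is assessment: the Investigator judges the intensity and relatedness of unsolicited events, which belong to the third primary safety endpoint in Section 5.4. Relatedness also determines whether the halting rules in Section 7.2 are met.

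**Working it through.** **Step 1. The chain of rules.**

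| Link | Source | Does any section break it? |
|---|---|---|
| A dosed subject's code is opened | 9.3 (emergency or escalation decision); 7.1 (SRC) | No; it is expressly allowed |
| That subject leaves | 9.13, where safety is one of the listed grounds | No; but leaving is not automatic after a code break |
| The subject is replaced | 9.13 exception, Sponsor's discretion | The default forbids it; the exception does not carve out opened codes |
| The replacement gets the same arm | 9.4 | No; stated without exception |
| The newcomer can be matched to the original | 9.4: number plus 100 in Part 1. In Part 2, by knowing who is being replaced | No |

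If all the links occur, the newcomer's arm is certain to whoever saw the original's code. Nothing in the protocol requires a different allocation or hides the connection.

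**Step 2. Cohort sizes, and what a blinded assessor otherwise knows.** The sizes in Section 8.2 reproduce the planned total: 32 + 32 + 56 + 32 + 32 + 32 = 216.

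- Cohorts 1, 2, 4, 5 and 6: 24/32 = 75% chance of active.
- Cohort 3: (24 + 24)/56 = 48/56 = 85.7% chance of active.

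For the replacement of an unblinded subject, these become 0% or 100%. In Cohort 3 the opened code also separates Treatment C from Treatment D.

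**Step 3. Weight of one subject.** 1/24 = 4.2% of an active group; 1/8 = 12.5% of one cohort's placebo group. These are shares of a group, not estimates of bias. The protocol gives no expected number of code breaks or replacements, so no expected count can be computed.

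**Step 4. The protocol's own example.** Numbers 1001 and 1002 belong to the Cohort 1 sentinels (Section 9.4), whose early safety data go to the SRC before the rest of the cohort is dosed (Section 7.1). In Cohort 3, Section 6 fixes the two sentinels as one placebo and one active on Treatment C. There, opening one sentinel's code reveals the other's, and so that of a replacement for either.

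**The case against.** The strongest reply is that this is a rare case reached only through an exception. Replacement after dosing is barred by default. If it takes the number dosed above plan it must be documented in an amendment, and Section 13.1 requires ethics approval before an amendment is implemented unless the change is only logistical or administrative. Ordinary replacement, before dosing, leaves no post-dose reactions to learn from. The same-treatment rule also has a stated and sensible purpose, to hold the allocation ratio. All of this stands and keeps the point small. It does not close the gap, because an amendment records the extra dosing without concealing the allocation.

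A reader might infer more than the text supports:

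- **That the Sponsor always learns the arm.** For an emergency code break, Section 9.3 says only that the Sponsor is contacted. Sponsor knowledge is firm only where the SRC opens a code. The envelope may also be opened by a physician other than the Investigator.
- **That the linked number alone unblinds staff who saw the original's reactions.** No reactogenicity rates are given, and the chance of active is already 75% to 86%. Inferring the arm this way is speculative. The numbering rule also appears only in the Part 1 paragraph.
- **That the primary safety endpoints as a whole are compromised.** Solicited events, two of the three primary safety bullets, are graded by the subjects (Section 9.15.2), who stay blinded. Local reactions are checked by an observer blind to the randomisation scheme (Section 9.10.8).
- **That the antibody endpoints are affected.** Serum is analysed by laboratory staff blind to treatment and visit (Section 11.2).

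**Conclusion.** The point holds in a limited form. Sections 9.13, 9.4, 9.3 and 7.1 together allow a replacement to enter with a treatment already known to whoever learned the original's code. That is contrary to the blinding Section 9.3 requires of those who evaluate adverse events. The safety exception there justifies opening the code of the person at risk and gives no ground for knowing the arm of a new volunteer.

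The exposure is mainly to intensity and relatedness ratings of unsolicited events and to the relatedness calls behind the halting rules. Safety reporting is descriptive, with no inferential analysis planned (Section 11), so no formal test is at risk.

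The conclusion assumes that a dosed subject's code is opened, that the subject leaves, that the Sponsor uses the exception, and that a person who knows the code then selects or assesses the replacement. The number affected is probably very small. The change is still worth making, because the groups have 24 and 8 subjects and a few sentences remove the problem.

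**What to change.** In Sections 9.13 and 9.4, state three things:

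1. A dosed subject whose treatment code has been broken is not replaced under the inherited-allocation rule.
2. Any discretionary decision to replace is made without reference to treatment.
3. Other replacements keep the original's treatment, but the unblinded pharmacy gives them a number from a reserve list that does not identify the original.

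The first statement does most of the work. The third helps less when only one subject has left, because staff can then guess who is being replaced.

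Randomising the replacement afresh is not advised. It would give up the ratio that Section 9.4 sets out to keep. In Cohort 3, a fresh draw in the 24:24:8 ratio would assign Treatment D with probability 24/56 = 42.9%, which could break the sentinel pairing fixed in Section 6.

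The cost is that a group may end one subject short (23 rather than 24 on active, or 7 rather than 8 on placebo in a cohort), and that a short reserve list must be prepared. No dose, schedule or stopping rule changes.
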